## 2. SYNOPSIS

Trial Title	Feasibility study of sentinel lymph node mapping in rectal cancer	
Internal ref. no. (or short title)	SentiRect Study	
Trial Design	Feasibility: proof of principle	
Trial Participants	Rectal cancer patients	
Planned Sample Size	40 patients	
Treatment duration	Single pre-operative administration	
Follow up duration	2-3 weeks	
Planned Trial Period	12 months	
	Objectives	Outcome Measures/Endpoints
Primary	
Establish feasibility of identifying sentinel lymph node in rectal cancer:
 
[A] Adverse or hypersensitivity reactions after Sienna+ tracer injection in rectal cancer patients.
 
[B] Establish whether tracer is still present and detectable at the tumour injection site and in the lymph nodes at the time of surgery.
 
[C] Determine the impact of Sienna+ injection on subsequent
	
[A] Frequency of adverse or hypersensitivity reaction.
 
[B] Frequency of tracer being detectable at the tumour injection site and in the lymph nodes at the time of surgery.
 
[C] Surgeon's assessment of any difficulties encountered

	surgery (e.g. any difficulties due to discolouration or inflammation of tissue planes)	attributable to prior Sienna+ injection.
Secondary	
[A] Correlate histopathology findings with tracer uptake in the lymph nodes.
 
[B] Radiologically evaluate the drainage pattern of Sienna+ tracer using a high resolution MRI, to establish a baseline for individual variation.
 
EX-VIVO part of study:
 
[C] Measure the distribution and spread of the Sienna+ tracer using the SentiMag hand-held probe in mesorectal specimen after rectal cancer surgery (in the pathology department). This is to establish a baseline in individual variation between specimens.
 
[D] Assess the accuracy of the SentiMag hand-held probe/Sienna+ tracer in identifying "sentinel" lymph nodes. This will be determined in conjunction with a pathologist who will systematically identify lymph nodes in the standard manner. The level of tracer activity in each lymph node will be measured and correlated with position and tumour cell involvement.
 
IN-VIVO part of study:
 
[E] Establish feasibility of sentinel lymph node biopsy during localised surgery for early rectal cancer using SentiMag hand-held probe to identify "peaks" of tracer activity intro-operatively.
	
[A] Correlation between histopathology findings and tracer uptake (determined by Sentimag probe) in the lymph nodes.
 
[B] High-resolution MRI mapping of the drainage pattern of Sienna+ tracer.
 
EX-VIVO part of the study:
 
[C] Mapping of the distribution of Sienna+ tracer in the mesorectal specimen using the SentiMag hand-held probe after rectal cancer surgery.
 
[D] Accuracy of the SentiMag hand-held probe/Sienna+ tracer in identifying "sentinel" lymph nodes, determined by correlation with histopathology findings.
 
IN-VIVO part of study:
 
[E] Number of TEM operations where the "sentinel" lymph node could be identified during surgery using the Sentimag probe, and then successfully removed.

Device name	Magtrace® tracer and SentiMag® magnetometer	
Device Manufacturer	Endomagnetics, Cambridge	
Device Classification	Class IIa device	

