
with a pathologist who will systematically identify lymph nodes in the standard manner. The level of tracer activity in each lymph node will be measured and correlated with position and tumour cell involvement.
 
IN-VIVO part of study:
 
[E] Establish feasibility of sentinel lymph node biopsy during localised surgery for early rectal cancer using SentiMag hand-held probe to identify "peaks" of tracer activity intra-operatively.
	
findings.
 
IN-VIVO part of study:
 
[E] Number of TEM operations where the "sentinel" lymph node could be identified during surgery using the Sentimag probe, and then successfully removed.

Tertiary Objectives Not applicable
	
Not applicable

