Intra-operative detection of the sentinel lymph node using the SentiMag probe and excision of the identified node (second part participants only): During rectal cancer surgery, following excision of the tumour, the surgeon will use the hand held SentiMag probe to identify the sentinel lymph node. This will then be dissected and removed for subsequent histological analysis.

Post-operative monitoring: Following surgery patients will be admitted to the colorectal ward for routine post-operative care. During this time they will be monitored and any adverse reactions or post-operative complications will be recorded. The patients’ participation in the study will cease when they are discharged from hospital.

Ex-vivo detection of the sentinel lymph node in the surgical specimen using the SentiMag probe (first part only): The SentiMag probe will be used to measure the distribution of the tracer and to identify the sentinel lymph node in the specimen removed during the standard surgical procedure. A Near InfraRed (NIR) imaging system will also be used to assess the specimen to detect the distribution of ICG as an adjunct to identifying lymph nodes.

Ex-vivo histological assessment of the surgical specimen: A colorectal pathologist will examine the tissue removed during surgery to identify all the lymph nodes present and whether or not they contain metastatic cancer deposits, according to standard practice. At the conclusion of the study the samples will be held in the cellular pathology department, in line with standard practice for diagnostic surgical specimens.

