## **8.4. Randomisation, blinding and code-breaking**

Not applicable

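### In the ex-vivo part, no step keeps node harvest and histology, the reference for probe accuracy, independent of the probe and ICG findings

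*Combined protocol and SAP*

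**What the plan says.** Two secondary outcomes set probe readings against histology. Outcome A is "Correlation between histopathology findings and tracer uptake (determined by Sentimag probe) in the lymph nodes". Outcome D, confined to the ex-vivo part, is the accuracy of the probe and "tracer in identifying 'sentinel' lymph nodes, determined by correlation with histopathology findings". The objective behind D (synopsis, repeated in section 5) adds: "This will be determined in conjunction with a pathologist who will systematically identify lymph nodes in the standard manner". It continues: "The level of tracer activity in each lymph node will be measured and correlated with position and tumour cell involvement". Under objective C, the ex-vivo probe work takes place in the pathology department.

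Section 8 describes the ex-vivo work in two paragraphs. The first has the probe map the tracer and find the sentinel node in the specimen, with near-infrared (NIR) imaging of ICG as a further aid to finding nodes. The second has a colorectal pathologist examine the tissue "to identify all the lymph nodes present and whether or not they contain metastatic cancer deposits", following usual practice.

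Section 8.4, headed "Randomisation, blinding and code-breaking", reads in full "Not applicable". Section 12.1 calls a node positive when its activity exceeds 10% of that at the injection site, and compares nodes with pathology by an unspecified correlation. Section 12.2 gives accuracy of sentinel node detection as the reason for recruiting the 20 ex-vivo patients.

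**The concern.** When one test is judged against another, the reference result should be reached without knowledge of the test result. Here the pathologist's harvest decides which nodes enter the comparison, and the histology decides which of them contain tumour. The plan has the pathologist take part in determining accuracy and lists the probe and NIR work first. It has no rule that keeps those findings from the person who harvests and reads the nodes. A single-arm design makes randomisation and code-breaking irrelevant, but not the masking of an assessor.

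Two mechanisms are possible. Hot nodes could be sectioned or read more closely than cold ones, or hot nodes could be found more often than cold ones. Either can flatter the probe. The serious error for a staging biopsy is tumour in a cold node when the hot node is clear. If that tumour is missed, a false negative is counted as a true negative. Section 4 states that a clinical trial of sentinel node biopsy is intended next, so the accuracy result will be carried forward.

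**Working it through.** The plan gives no accuracy target, effect size or calculation for this outcome (section 12.3 marks significance as not applicable), so there is no figure to reproduce. The check asks which mechanism moves which measure, and how far.

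**Inputs, all assumed, since the documents give none.** 300 nodes: N_h = 40 hot and N_c = 260 cold. True tumour prevalence (p_h, p_c): 10% in both groups (no link), or 20% hot and 8% cold (true link). Harvest probabilities h_h, h_c and histological detection rates s_h, s_c vary as shown.

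**Expected counts.** a = N_h·h_h·p_h·s_h (hot, tumour found); b = N_h·h_h − a; c = N_c·h_c·p_c·s_c (cold, tumour found); d = N_c·h_c − c.

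**Measures.** Odds ratio = ad/(bc). Node-level sensitivity = a/(a + c). Phi = (ad − bc)/√[(a+b)(c+d)(a+c)(b+d)].

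In the odds ratio, node counts and harvest probabilities cancel. It equals [p_h·s_h/(1 − p_h·s_h)] / [p_c·s_c/(1 − p_c·s_c)], so only unequal histological detection can distort it.

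**1. Masked reading** (harvest 0.80 and detection 0.85 in both groups).
- No link: a = 40 × 0.80 × 0.10 × 0.85 = 2.72; c = 260 × 0.80 × 0.10 × 0.85 = 17.68. Odds ratio 1.00; sensitivity 2.72/20.40 = 13.3%.
- True link: odds ratio (0.17/0.83)/(0.068/0.932) = 2.81; sensitivity 5.44/19.584 = 27.8%; phi 0.127.

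**2. Unequal histological scrutiny** (harvest equal).

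| Detection, hot v cold | Odds ratio, no link | Odds ratio, true link |
|---|---|---|
| 0.85 v 0.85 | 1.00 | 2.81 |
| 0.90 v 0.85 | (0.090/0.910)/(0.085/0.915) = 1.06 | 3.01 |
| 0.95 v 0.80 | (0.095/0.905)/(0.080/0.920) = 1.21 | 3.43 |
| 0.95 v 0.70 | (0.095/0.905)/(0.070/0.930) = 1.39 | 3.95 |

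**3. Probe-guided harvest alone** (1.0 hot v 0.6 cold, detection 0.85 in both).
- No link: odds ratio stays 1.00; sensitivity 3.40/(3.40 + 13.26) = 20.4%, against 13.3%.
- True link: odds ratio stays 2.81; sensitivity 6.80/(6.80 + 10.608) = 39.1%, against 27.8%. Phi rises from 0.127 to 0.145, so a correlation coefficient can move even though the odds ratio does not.

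**4. Both together** (harvest 1.0 v 0.6, detection 0.95 v 0.70). Odds ratio 1.39 with sensitivity 25.8% (no link), or 3.95 with 46.5% (true link).

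**5. Patient level.** Suppose 4 to 8 of the 20 patients are node-positive and exactly one has tumour only in a cold node. The false-negative rate is then 1/4 = 25% to 1/8 = 12.5%. If that one deposit is missed, it becomes 0/3 to 0/7, that is 0%.

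**The case against.** The plan is silent on masking, and silence is not evidence of joint or biased reading. A reader might infer that histology is read together with the probe by an openly unblinded pathologist. The documents do not say so. Section 8 makes histology a separate paragraph covering all nodes under usual practice, and the joint wording in the synopsis concerns node identification. The entry in section 8.4 answers a combined heading in a non-randomised study and is no statement about the pathologist. Nor does any text suggest that a node already known to hold tumour would be probed again. All of this stands. Usual practice is a partial safeguard, but it does not conceal the probe or NIR findings.

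A reader might also infer that the results must be biased upward. That is too strong: harvest guided by the probe leaves the odds ratio alone, and the mechanism that inflates it needs unequal scrutiny, which would depart from the described procedure.

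Sampling error may also exceed the bias. Take complete harvest, 10% prevalence in both groups, and detection of 95% hot v 75% cold. Then 3.8 of 40 hot nodes and 19.5 of 260 cold nodes are positive, a ratio of 0.095/0.075 = 1.27 with a rough 95% interval of 0.4 to 3.6, ignoring clustering within patients. This also stands, but imprecision does not remove a bias that can be avoided cheaply.

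Finally, harvesting before any probing would defeat the intact-specimen mapping of outcome C. That is right, and the fix has to put the mapping first.

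**Conclusion.** The point holds as a gap in the ex-vivo procedure: nothing makes the harvest or the histological reading independent of the probe and ICG findings. The consequence is possible upward bias, not certain bias. With no true link, the illustrated odds ratio runs from 1.06 to 1.39; with a true link, 2.81 becomes 3.01 to 3.95. Guided harvest affects sensitivity and phi instead. These sizes rest wholly on assumed prevalence, harvest and detection rates; the sensitivities and phi also depend on the assumed node counts.

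The point concerns secondary outcomes of a feasibility study, and the primary outcomes are untouched. It merits a cheap improvement because outcome D is the stated purpose of half the sample. It should not be extended to the in-vivo part, although outcome A spans both parts. There, only the node identified by the probe is described as removed, which is a separate question of verification.

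**What to change.** Add a short paragraph to section 8, and replace the entry in section 8.4 with a statement on assessor masking:

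1. The investigator trained on the probe does the intact-specimen probe and NIR mapping for outcome C first, and withholds the results.
2. The pathologist completes the standard harvest and numbers every node.
3. The investigator records the probe reading of each numbered node before histology is known.
4. All nodes are sectioned and read by the same standard protocol.
5. Readings and images stay withheld from the reporting pathologist until nodal status is signed off.
6. Any node found only by a later probe- or ICG-guided search is flagged and analysed separately.

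The cost is some extra coordination in pathology and one CRF sheet. No extra staff should be needed: section 8 already trains the principal investigators on the probe, and section 8.1 lists pathologists among the colleagues they meet with, not as the investigators themselves. No patient visit or treatment changes. Section 9.1 describes the tracer as dark brown, so masking will be incomplete where pigment is visible; report this as a limitation.

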## 5. OBJECTIVES AND OUTCOME MEASURES/ENDPOINTS

Objectives	Outcome Measures/Endpoints

Primary Objectives
 
Establish feasibility of identifying sentinel lymph node in rectal cancer:
 
[A] Adverse or hypersensitivity reactions after tracer injection in rectal cancer patients.
 
[B] Establish whether tracer is still present and detectable at the tumour injection site and in the lymph nodes at the time of surgery.
 
[C] Determine the impact of tracer injection on subsequent surgery (e.g. any difficulties due to discolouration or inflammation of tissue planes
	
[A] Frequency of adverse or hypersensitivity reaction.
 
[B] Frequency of tracer being detectable at the tumour injection site and in the lymph nodes at the time of surgery.
 
[C] Surgeon’s assessment of any difficulties encountered attributable to prior tracer injection

Secondary Objectives
 
[A] Correlate histopathology findings with tracer uptake in the lymph nodes.
 
[B] Radiologically evaluate the drainage pattern of tracer using a high resolution MRI, to establish a baseline for individual variation.
 
EX-VIVO part of study:
 
[C] Measure the distribution and spread of the tracer using the SentiMag hand-held probe in mesorectal specimen after rectal cancer surgery (in the pathology department). This is to establish a baseline in individual variation between specimens.
 
[D] Assess the accuracy of the SentiMag hand-held probe/ tracer in identifying "sentinel" lymph nodes. This will be determined in conjunction
	
[A] Correlation between histopathology findings and tracer uptake (determined by Sentimag probe) in the lymph nodes.
 
[B] High-resolution MRI mapping of the drainage pattern of tracer.
 
EX-VIVO part of the study:
 
[C] Mapping of the distribution of tracer in the mesorectal specimen using the SentiMag hand-held probe after rectal cancer surgery.
 
[D] Accuracy of the SentiMag hand-held probe/ tracer in identifying "sentinel" lymph nodes, determined by correlation with histopathology

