## **12. STATISTICS**

### **12.1. Description of Statistical Methods**

All data will be stored in an Excel worksheet and analysed using Excel and R.

Frequency of event (adverse, hypersensitivity or complication) will equate to: number of adverse event/total number of recruited patients.

Frequency of tracer detection at surgery (at tumour site and in lymph nodes) will equate to: number of operations where tracer seen/ total number of operations on recruited patients.

Impact of tracer injection on subsequent surgery will be assessed by the surgeon's binary assessment as to whether surgery was more difficult than expected, and also free text comments to be analysed qualitatively.

A sentinel lymph node will be defined as the first lymph node draining the tumour and positivity defined according to the manufacturer's instructions. A "positive" node will be defined as having over 10% of the tracer activity of the site of initial submucosal injection. A "negative" node will be defined as having less than 10% of the tracer activity of the site of initial submucosal injection.

The detection rate for sentinel lymph nodes on MRI scan and Sentimag probe assessment will equate to: number of patients/specimens in whom a sentinel lymph node is identified/total number of examined patients/specimens.

MRI and Sentimag mapping will be qualitatively compared for all relevant patients/specimens (as appropriate) to establish a baseline of individual variability.

The presence and location of lymph nodes in the mesorectal specimen will be compared with the pathology findings for each patient in the ex-vivo part using correlation.

The success rate for removing the sentinel lymph node during TEM surgery will equate to: number of patients in whom the sentinel lymph node was removed/total number of patients undergoing TEM operation.

As this is a feasibility study, results will be continuously evaluated and adjustments made to the tracer dosage and timing of injection if indicated.

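### Secondary outcome D measures accuracy of sentinel node identification by correlation with histology, which mixes accuracy with case mix; no false-negative rate is defined

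*Combined protocol and SAP*

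**What the plan says.** All references are to the combined protocol and SAP.

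- **Outcome D** (section 2, repeated in section 5) is "Accuracy of the SentiMag hand-held probe/Sienna+ tracer in identifying 'sentinel' lymph nodes, determined by correlation with histopathology findings". The matching objective in section 5 explains what is correlated: "The level of tracer activity in each lymph node will be measured and correlated with position and tumour cell involvement".
- **Outcome A** is "Correlation between histopathology findings and tracer uptake (determined by Sentimag probe) in the lymph nodes", which is almost the same statistic without the word accuracy.
- **Sentinel node** (section 12.1): "A sentinel lymph node will be defined as the first lymph node draining the tumour". The same sentence refers positivity to the manufacturer's instructions, which are not among the documents. The tracer threshold follows at once: "A 'positive' node will be defined as having over 10% of the tracer activity of the site of initial submucosal injection".
- **Rates defined in section 12.1** for sentinel nodes are a detection rate, "number of patients/specimens in whom a sentinel lymph node is identified/total number of examined patients/specimens", and a removal rate for TEM operations.
- **Comparison with pathology in the ex-vivo part** (section 12.1): "The presence and location of lymph nodes in the mesorectal specimen will be compared with the pathology findings for each patient", by correlation. No coefficient is named. No false-negative rate, sensitivity or predictive value is defined anywhere.
- **Purpose and size** (section 12.2): 20 ex-vivo patients, recruited to establish how accurately sentinel nodes are detected. The number rests on precedent studies.

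**The concern.** Histology shows whether a node contains tumour. It does not show whether that node drains the tumour first. Under the drainage definition, two kinds of correct result count against the tracer when its signal is correlated with tumour status:

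1. a hot, tumour-free node in a patient with no nodal metastasis;
2. a cold metastatic node further along the chain from a correctly marked sentinel node.

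The coefficient therefore moves with the number of patients who have nodal metastasis, with how far the disease has spread among the nodes, and with how many nodes take up tracer, even if the method never misses. A reader of the ex-vivo results would want to know how often the sentinel nodes are clear while another node is metastatic. The planned statistic does not answer that.

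A smaller point concerns the label. Section 12.1 gives a drainage concept and a 10% tracer threshold, but the protocol text does not say whether every node over 10% counts as sentinel. That choice can change a false-negative rate.

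**Working it through.** **The plan's own figure.** The 20 ex-vivo patients cannot be reproduced by calculation. Section 12.2 gives no target rate or precision, and section 12.3 sets no significance level.

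**Inputs.** From the plan: 20 patients and the 10% threshold. Assumed, because the documents give no values: 15 nodes per patient (300 in all), 2 hot nodes per patient (40 in all), and the numbers of metastatic nodes below. The plan names no coefficient, so phi on hot/cold by metastatic/tumour-free serves as an example.

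phi = (ad − bc) / √[(a+b)(c+d)(a+c)(b+d)], where a = hot metastatic, b = hot tumour-free, c = cold metastatic, d = cold tumour-free.

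**Step 1. No misses, increasing spread.** Eight patients have nodal metastasis, each with one metastatic hot node.

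| Further cold metastatic nodes per such patient | (a, b, c, d) | phi | Patients missed |
|---|---|---|---|
| 0 | (8, 32, 0, 260) | 2080/√(40·260·8·292) = 0.42 | 0/8 |
| 1 | (8, 32, 8, 252) | 1760/√(40·260·16·284) = 0.26 | 0/8 |
| 2 | (8, 32, 16, 244) | 1440/√(40·260·24·276) = 0.17 | 0/8 |

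This does not come from dichotomising. With tracer level simulated as continuous (hot uniform on 10–60%, cold uniform on 0–10% of the injection site), mean Pearson r is about 0.37, 0.22 and 0.15.

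**Step 2. Wider case mix, still no misses.** The lowest case has 4 patients with nodal metastasis, each with 1 metastatic hot and 2 cold metastatic nodes: (4, 36, 8, 252), phi = 0.12. The highest has 10 such patients, each with both hot nodes metastatic and no cold metastases: (20, 20, 0, 260), phi = 0.68.

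**Step 3. Same phi, different accuracy.**
- Six patients with one metastatic hot node each, none missed: (6, 34, 0, 260), phi = 0.364. False-negative rate 0/6 (exact 95% CI 0–46%).
- Four patients with both hot nodes metastatic, and two missed patients with one cold metastatic node each: (8, 32, 2, 258), phi = 0.364. False-negative rate 2/6, or 33% (4–78%).

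**Step 4. Limit of the argument.** Hold the 8 patients at one metastatic node each and miss 2: (6, 34, 2, 258), phi = 0.30, against 0.42 with none missed. At fixed case mix the coefficient does respond to misses.

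**Step 5. Effect of the sentinel rule.** In the first row of step 1, counting every node over 10% gives 0/8 missed (0–37%). Counting only the highest-reading node gives 4/8 (16–84%), if the metastatic node is the cooler of the two hot nodes in four of the eight.

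**Step 6. Precision and case-mix dependence of the replacement.**
- Exact 95% intervals with no misses: 0/4 gives 0–60% and 0/10 gives 0–31%.
- A tracer that labelled 2 of 15 nodes at random would miss a patient with m metastatic nodes with probability C(15−m, 2)/C(15, 2): 91/105 = 87% for m = 1, 66/105 = 63% for m = 3, 36/105 = 34% for m = 6. With 6 hot and 6 metastatic nodes it is C(9, 6)/C(15, 6) = 84/5005 = 2%.
- Negative predictive value at a fixed 25% false-negative rate, all patients having a sentinel node detected: with 4, 8 or 12 of 20 patients node-metastatic it is 16/17 = 94%, 12/14 = 86% or 8/11 = 73%.

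**The case against.** **The replacement also depends on case mix.** This is correct and must be disclosed. Step 6 shows that a patient-level false-negative rate varies with hot-node count and nodal spread, and that negative predictive value varies with prevalence. The false-negative rate is still the better measure, because it counts the patients for whom sentinel node biopsy would mislead and its denominator is explicit. It should be read beside the quantities that move it.

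**A sentinel rule exists.** A reader might infer that the plan has none. The documents do not support that: the drainage concept leads, through the manufacturer's instructions, straight into the 10% threshold, and the instructions may settle whether several hot nodes all count. What stands is that the protocol text does not tie the threshold to the word sentinel, so this part is a clarification.

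**The sizes are constructed.** Nodes per patient, hot nodes, prevalence and spread are all assumed. Phi is not named in the plan, and step 3 changes the number of metastatic hot nodes as well as the misses. Objective D also correlates with position, which the examples do not model, and the section 12.1 comparison may mean agreement on node location. The examples show that the coefficient can mislead, not by how much it will.

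**This is a feasibility study and the rate can be derived later.** Both are true and limit the severity. But section 12.2 names accuracy as the purpose of the ex-vivo patients, and a definition chosen after the results are seen carries less weight than one stated beforehand.

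**Conclusion.** The point holds. Correlation with histology, taken as accuracy, combines accuracy with nodal prevalence, nodal spread and the number of hot nodes, and no false-negative rate is defined for the stated purpose of the ex-vivo part. This conclusion follows from the plan's wording; the sizes shown rest on the assumed inputs.

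A reader might infer more: that the accuracy result would be uninterpretable, or that the study could reach a wrong go/no-go decision. The documents support neither. A conventional false-negative rate can be computed from data already planned, and outcome D is secondary with no threshold or decision attached. Severity is minor to moderate.

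**What to change.** Amend section 12.1, section 12.2 and outcome D in sections 2 and 5.

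1. **Accuracy measure.** Define a patient-level false-negative rate with an exact 95% CI: patients with nodal metastasis whose detected sentinel nodes are all tumour-free, divided by patients with nodal metastasis and at least one sentinel node detected.
2. **Sentinel rule.** State that, for this analysis, every node over the plan's 10% threshold counts as sentinel, after confirming that this is consistent with the manufacturer's instructions the plan cites. Report the number of such nodes per patient, and use the highest-reading node alone as a sensitivity analysis.
3. **Negative predictive value, if reported.** Restrict both parts to patients with a sentinel node detected: those whose detected sentinel nodes are all tumour-free and who have no metastatic node in the specimen, divided by those whose detected sentinel nodes are all tumour-free. Without the restriction on the numerator, the ratio could exceed 100%.
4. **Correlation.** Keep the node-level correlation as descriptive, under outcome A.
5. **Section 12.2.** State that the false-negative rate rests only on patients with nodal metastasis, will be imprecise (the intervals for 0/4 and 0/10 in step 6 show the scale), and varies with hot-node count and nodal spread, as negative predictive value does with prevalence. Report these quantities beside it.

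The cost is text only. Tracer level per node (objective D) and metastatic status of all nodes (section 8) are already to be collected, so no new data, patients or procedures are needed. The price is a more modest claim for what 20 ex-vivo patients can show.
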